#### **Part 4:**

The study will continue to Part 4 using the tolerable dose and schedule determined in Part 3.

#### **Parts 3 and 4:**

The dose of MT-3724 in all cohorts will be calculated based on the subject's baseline body weight (in kilograms [kg]). For MT-3724 dose calculation, the body weight will be measured before the first dose of MT-3724 in Cycle 1 (baseline for all subsequent assessments). If the body weight has changed by  $\geq 10\%$  from the baseline value, this will require re-calculation of MT-3724 dose or according to institutional policies should they require adjustment for any change in body weight.

**The total administered dose of MT-3724 must not exceed 1200  $\mu\text{g}$  per infusion for the 10  $\mu\text{g}/\text{kg}$  dose; 3000  $\mu\text{g}$  per infusion for the 25  $\mu\text{g}/\text{kg}$  dose and 6000  $\mu\text{g}$  per infusion for the 50  $\mu\text{g}/\text{kg}$  dose.**

The guidance for treatment modification (dose interruption / delay, dose reduction or treatment discontinuation) is presented in [Section 6.2](#).

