## 1.2 Study Schema

### 1.3 Schedule of Activities (SoA)

**Table 1-1. Schedule of Activities**

	SCR a	Treatment Period (21-day Cycles) b								EoT d	STFU e	LTFU f	Notes
		D1	D3	D5	D8	D10	D12	D15 c	D16-21				
General and Safety Assessments													
Informed consent	X												
Eligibility criteria	X												
Demography	X												
Physical exam	X	X								X			Complete physical exam at screening and EoT. Abbreviated exam D1 of every cycle. See Section 8.4.4 for details.
Height	X												
Weight	X	X	X	X	X	X	X	(X)		X	X		Body weight measured before the start of treatment on C1D1 will be used to calculate the MT-3724 dose in all subsequent cycles. The dose must be re-calculated when the body weight has changed by $\geq 10\%$ from the baseline value; or according to institutional policies should they require adjustment for any change in body weight. (X): Collected only if weekly dosing is implemented.
BMI	X												
Medical history	X												Illnesses that occurred at any time before the start of screening that, in the investigator's opinion, could increase the risk to subject and/or influence the study endpoints should be captured in the medical history as prior illnesses. Illnesses that are active at the time of informed consent should be captured in the medical history as concomitant illnesses.
NHL assessment	X												Initial diagnosis : include the type, histology, staging (Ann Arbor Classification-Cotswold Modification) and grading according to International Prognostic Index (IPI) for NHL At time of relapse : IPI and time to progression after first line of therapy (captured as date of first relapse/progression) Current status : additionally collect the genetic mutational status (eg, MYC, BCL2, and BCL6 rearrangement / overexpression) and molecular subtype (GCB vs ABC) (if available).

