## 2.2.2 Guidance to the Investigator for Capillary Leak Syndrome

Capillary leak syndrome typically occurs during earlier cycles of treatment. Capillary leak syndrome is suspected if the subject experiences at least 2 of the following signs and/or symptoms within the same cycle (unless unequivocally related to underlying condition):

- Hypoalbuminemia
- Hypotension
- Edema (peripheral or central, all types) and/or weight gain

Subjects should be closely monitored for signs and symptoms of CLS. This includes monitoring of vital signs (temperature, heart rate, blood pressure [BP], respiration rate), body weight and edema of any type including both peripheral edema and central edema (such as pleural effusion or signs of dyspnea), and monitoring of laboratory parameters including hemoconcentration (eg, hematocrit, Hb), and especially albumin and creatine phosphokinase (CK) in case of clinical symptoms indicative of CLS.

Refer to the MT-3724 CLS management guide.

Refer to [Section 6.2](#) for dose modification guidelines.

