**Table 6-4. MT-3724 Dose Modification Guidance and Specific Management of Toxicities**

	Specific Management	MT-3724 Dose Modificationa

Grade <math>\geq</math> 2 CLS: As defined in CTCAE v5.0, or if at least 2 of the following within the same cycle (unless unequivocally related to underlying condition) reaches the level of Grade 2:
 
 
• Hypoalbuminemia
 
• Hypotension
 
• Edema (peripheral or central, all types) and/or weight gain
 
	
Subjects should be closely monitored for signs of CLS. This includes:
 
 
• Monitoring of vital signs (temperature, heart rate, BP, respiration rate), body weight, edema of any type including both peripheral edema and central edema (such as pleural effusion or signs of dyspnea).
 
• Monitoring of laboratory parameters including hemoconcentration (eg, hematocrit, Hb), and especially albumin and CK in case of clinical symptoms indicative of CLS.
 
 
Investigators should consider supportive measures while on trial regardless of dosing or timing of dosing. If a subject experiences Grade 2 hypotension, orthostasis, edema, or hypoalbuminemia, normal saline and/or an albumin infusion may be given, as needed.
	
Treatment modification due to CLS:
 
 
• For Grade <math>\geq</math> 3 CLS, the MT-3724 treatment must be permanently discontinued.
 
• For Grade 2 CLS, the MT-3724 treatment must be held, and may only be restarted after: 
 
◦ a minimum of 7 days has elapsed after onset of CLS, and
 
◦ all signs and symptoms of CLS have resolved to at least grade 1, and
 
◦ albumin has remained <math>\geq</math> 3.0 g/dL for at least 5 days post last albumin infusion (if required) without additional albumin substitution
 
 
 
 
Subsequent doses of MT-3724 must be:
 
 
• reduced by at least 25%, and
 
• administered once weekly
 
 
or subject may be permanently discontinued at the investigator's discretion.

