#### **8.4.3 Physical Measurements**

Height (in meters [m]) and weight (in kilograms [kg]) will be measured; body-mass index (BMI) will be then be calculated.

The body weight measured before the start of treatment on C1D1 will be used to calculate the MT-3724 dose in all subsequent cycles. The dose must be re-calculated when the body weight has changed by  $\geq 10\%$  from the baseline value; or according to institutional policies should they require adjustment for any change in body weight.

All body weight measurements will contribute to the safety assessment. Unscheduled body weight measurements could be made for safety assessment at the investigator's discretion.

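### The 10% weight re-calculation rule has no exception for fluid gain, so below the Grade 2 capillary leak hold it raises the dose on a listed warning sign (minor)

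*Protocol*

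**What the plan says.** **The weight rule.** Section 6.1.1.2 (Parts 3 and 4) takes baseline weight as the dosing weight. It then says that a change of 10% or more "from the baseline value, this will require re-calculation of MT-3724 dose or according to institutional policies". Section 8.4.3 makes this mandatory: "The dose must be re-calculated when the body weight has changed by" 10% or more. The weight note in Table 1-1 is equally firm. Its only alternative is "or according to institutional policies should they require adjustment for any change in body weight", which can act sooner than the 10% trigger. None of the three places treats fluid differently from other weight.

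**The CLS signs.** Section 2.2.2 lists three sign groups: hypoalbuminemia, hypotension, and "Edema (peripheral or central, all types) and/or weight gain". CLS is suspected when two of the three occur in one cycle, "unless unequivocally related to underlying condition". The stated consequence is close monitoring, with pointers to the CLS management guide and to Section 6.2.

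**The hold.** Table 6-4 defines Grade 2 or higher CLS by two routes: "As defined in CTCAE v5.0, or if at least 2 of the following within the same cycle" reaches Grade 2. Then: "For Grade 2 CLS, the MT-3724 treatment must be held, and may only be restarted after" several conditions are met. Grade 3 or higher means permanent discontinuation. Below Grade 2 no CLS hold is mandatory. Sections 6.2 and 6.2.1 let the investigator delay or reduce, but do not require it.

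**The concern.** The same observation, a rising weight, has two meanings in this protocol. In the CLS guidance it is a possible warning sign. In the dosing rule it is an instruction to give more drug. Where the gain is fluid and the subject is below the Grade 2 hold, the mandatory text points towards a larger infusion, and only discretionary text points the other way.

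This matters here because of the sponsor's own reasoning. Section 12.1 explains the revised caps by an association between the total dose given and CLS, and Section 2.2.1 reports a Grade 5 CLS event in Part 3. A rule that raises total dose because of retained fluid runs against the purpose of those changes.

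**Working it through.** **Inputs.** Dose levels are 10, 25 and 50 µg/kg, with caps of 1200, 3000 and 6000 µg per infusion (Table 6-1, Section 6.1.1.2). The trigger is a 10% change. Body weights are assumptions, since the documents give none.

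**Step 1: reproduce the caps.** 1200/10 = 3000/25 = 6000/50 = 120 kg. This matches the 120 kg basis given in Section 12.1.

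**Step 2: dose after a 10% gain.** Dose = min(weight × level, cap).

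| Baseline weight | 10 µg/kg | 25 µg/kg | 50 µg/kg |
|---|---|---|---|
| 60 kg | 600 to 660 (+60) | 1500 to 1650 (+150) | 3000 to 3300 (+300) |
| 70 kg | 700 to 770 (+70) | 1750 to 1925 (+175) | 3500 to 3850 (+350) |
| 100 kg | 1000 to 1100 (+100) | 2500 to 2750 (+250) | 5000 to 5500 (+500) |

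All entries are in µg, and each rise is exactly 10%. A gain just short of 10% changes nothing unless local policy adjusts for it.

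**Step 3: where the caps bite.** 120/1.10 = 109.1 kg, so the full 10% passes through up to about 109 kg. At 50 µg/kg:
- 110 kg: 5500 to 6000, +9.1%
- 115 kg: 5750 to 6000, +4.3%
- 120 kg: 6000 to 6000, nil

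**Step 4: sites that adjust for any change.** A 5% gain at 70 kg and 25 µg/kg takes 1750 to 1837.5 µg (+87.5).

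**Step 5: context.** Baseline weights of 60 to 100 kg already give a 67% spread in total dose at one level (100/60 = 1.67). The planned step-ups are 2.5-fold (25/10) and 2-fold (50/25).

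**Step 6: what else would catch the subject.**
- Adverse events are evaluated before every infusion in all cycles (Synopsis, Study Treatment).
- Local albumin is reviewed before all 6 Cycle 1 doses (Table 1-1).
- Albumin is also in the chemistry panel (Table 10-1), scheduled on Days 1 and 8. That covers 2 of 6 doses in Cycle 2 and 2 of 3 doses per cycle from Cycle 3. Section 10.2.1 calls for local chemistry if central results will not be ready before dosing.
- The schedule is not the whole of it. The albumin note in Table 1-1 also calls for additional albumin, as clinically indicated, in subjects with signs and symptoms of CLS. A subject with edema and a 10% gain has such a sign.
- Section 8.4.3 adds: "All body weight measurements will contribute to the safety assessment".

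Each control may lead an investigator to pause. None says that the dose should not be re-calculated upward on fluid weight.

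**The case against.** The strongest reply is that the affected group may be very small. It needs a fluid gain of 10% or more (7 kg at 70 kg) without Grade 2 CLS by either route, and the CTCAE route cannot be judged because its definition is not in the documents. The CLS management guide and the Pharmacy Manual, where a site would look, were not available either. Section 6.1.1.2 itself points to Section 6.2, and the note to Table 6-4 encourages contact with the sponsor or medical monitor where the recommendations do not fit. Section 12.1 places all CLS events within a few days of first dosing, or of re-dosing after CLS. Early on, albumin is reviewed before each dose and the first two doses are only 10 µg/kg. After Grade 2 CLS the dose must fall by at least 25%, so a 10% re-calculation would still leave it 17.5% below the previous total (0.75 × 1.10 = 0.825).

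Most of this stands, and it is why the point is minor. It does not remove the point: discretion to reduce does not override a stated duty to re-calculate, and the text does not say which prevails.

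A reader might infer that the protocol makes sites give more drug to a subject with established CLS. It does not: Grade 2 requires a hold and Grade 3 or higher a permanent stop. A reader might also link the fatal event to weight re-calculation. The documents record it at 50 µg/kg/dose in Part 3 and say nothing about weight.

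**Conclusion.** The point holds in a narrow form. For a subject whose gain is fluid and who is below the Grade 2 CLS hold, the weight rule as written raises the total dose in proportion to the gain, within the caps, unless the investigator chooses otherwise.

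It would be tempting to go on to say that this materially raises CLS risk. The documents do not support that. The association with total dose is not quantified, there is no figure for CLS risk per 10% of dose, and nothing shows how often such gains occur. The conclusion rests on the protocol text alone and on assumed body weights. The severity is minor and the confidence low to moderate. No statistical figure in the plan is affected.

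**What to change.** Add one sentence to Section 6.1.1.2, Section 8.4.3 and the Table 1-1 weight note:

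> The dose is not re-calculated upward, including under institutional policy, for weight gain that the investigator attributes to or suspects is fluid retention or CLS (for example, with edema, hypoalbuminemia or hypotension that is new or worse than at baseline, unless unequivocally due to the underlying condition); Section 6.2 applies and the medical monitor is contacted.

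Tying the signs to change from baseline avoids catching subjects who entered with mild edema or low albumin. Naming institutional policy settles which rule prevails. Downward re-calculation and re-calculation for non-fluid gain stay as they are, and other upward changes need no separate documentation. If the CLS management guide already covers this, a cross-reference in the three places is enough.

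No new visit or measurement is needed, because weight is already taken on dosing days and adverse events are already evaluated before each infusion. The downside is under-dosing if a true gain is misread as fluid. After a true 10% gain the dose would be 50/1.10 = 45.5 µg/kg or 25/1.10 = 22.7 µg/kg, which is 9.1% below nominal. That is less than the first reduction step of about 25% in Table 6-3.

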##### **6.1.1.3 Dose Schedule**

All doses of MT-3724 will be administered as IV infusion over 1 hour (window = 54 to 75 minutes) in a 21-day cycle according to the schedule specified in each cohort ([Table 6-1](#)).

NOTE: Each dose of MT-3724 must be preceded by premedication administered within 60 minutes before the start of each infusion (see [Section 6.1.2](#))

All doses should be administered within the first 16 days of the 21-day cycle. For Cycle 1 and 2 doses are preferably administered on Days 1, 3, 5, 8, 10, and 12 ( $\pm 1$  d). For Cycle 3 and later doses are preferably administered on Days 1, 8, and 15. All cycles should use the following guidelines:

- The first 3 doses of Cycle 1 must be administered at least 2 days (approximately 48 hours) apart.
- All subsequent doses must be at least 20 hours apart (more than 5 half-lives of MT-3724 in serum), and must not be administered on more than 2 consecutive days.

The first dose of the first cycle will require approximately 5 hours in the clinic which include approximately 4 hours of post-dose safety assessments. Subsequent doses will require approximately 3 hours in the clinic which include approximately 2 hours of safety assessments post-dose (see also [Section 1.3, Schedule of Activities \(SoA\)](#)).

No more than 14 days should elapse between cycles. If more than 14 days elapse, the investigator must consult with the medical monitor before initiating the next cycle of treatment. Refer to [Section 6.2](#) for dose modification guidelines and management of toxicities.

Treatment will continue until death, disease progression, unacceptable toxicity, withdrawal of consent, or another reason for withdrawal, or until study discontinuation.

#### **6.1.1.4 Treatment Beyond Progression**

For subjects who have radiological, but not clinical, evidence of disease progression within 3 months of C1D1, in lieu of discontinuation, the investigator may continue treatment at the dose they are given at the time progression is identified if s/he believes the benefit outweighs the risk and provided the conditions identified below are met.

##### Conditions for continued treatment:

- absence of symptoms and signs, including worsening of laboratory values, indicating unequivocal PD,
- no decline in Eastern Cooperative Oncology Group performance status (ECOG PS) due to PD,
- absence of tumor progression at critical anatomical sites (eg, leptomeningeal disease),
- subject's written consent to defer any standard treatment options that may exist in favor of continuing MT-3724 treatment at the time of initial progression.

Radiological assessments should be repeated in 4 to 6 weeks from the time of initial progression.

#### **6.1.2 Other Protocol-required Intervention**

##### **Premedication Before MT-3724 Infusion**

Premedication as described in [Table 6-2](#) must be given within 60 minutes before the start of each MT-3724 infusion. The specific drugs in each of the 3 classes listed below can be selected at the investigator's discretion or according to the institutional guideline. Cases where a subject has a contraindicating medical condition that precludes pre-treatment with any of the categories below must be discussed with the Medical Monitor.

**Table 6-2. Premedication**

Premedication Class	Cycle 1	Cycle 2	Cycle 3+
Oral anti-pyretic agent	325-1000 mg acetaminophen (or equivalent)	325-1000 mg acetaminophen (or equivalent)	325-1000 mg acetaminophen (or equivalent) 
Intravenous H1 histamine receptor antagonist	50-100 mg diphenhydramine (or equivalent)	50-100 mg diphenhydramine (or equivalent)	50-100 mg diphenhydramine (or equivalent) 
Intravenous corticosteroid agent with a short biological half-life	250-1000 mg methylprednisolone (or equivalent)	250-1000 mg methylprednisolone (or equivalent) 	250-1000 mg methylprednisolone (or equivalent) 

 Dose adjustment permitted following MM approval.

### 6.1.3 Excluded Treatments, Medical Devices, and/or Procedures During Study Period

The following treatments are prohibited during the study:

- All systemic treatment for lymphoma
- Radiation therapy to tumor lesions that would serve as target lesions (measurable disease). Palliative radiation therapy to non-target lesions may be permitted (see [Section 6.5](#)).
- Systemic immune modulators, unless used for a treatment-emergent adverse event (TEAE) or as a premedication for MT-3724.
  - The immune modulators include, but are not limited to, systemic corticosteroids at doses > 20 mg/day or prednisone equivalent for more than 1 week, cyclosporin and tacrolimus.
- Any live vaccines from 4 weeks before the start of treatment, during the treatment and after the last dose of MT-3724 while peripheral B cells are depleted.

## 6.2 Dose Modification

The investigator may modify the MT-3724 treatment in an individual subject by:

- Dose interruption defined as changes made during the current dose (eg, temporary or permanent stop the IV infusion).
- Dose delay will be used for changes to dose schedule (eg, postpone the date of the next dose). A maximal dose delay of 14 days is allowed, a delay exceeding 14 days should be discussed with the medical monitor.
- Dose reduction (according to [Table 6-3](#))
  - Medical monitor must be notified when dose is reduced.
- Permanent discontinuation.

Refer to [Table 6-4](#) for guidance on dose modification of MT-3724 treatment (dose interruption, dose delay, dose reduction or permanent discontinuation) if deemed at least possibly related to MT-3724 by the investigator. Except where expressly prohibited (see [Section 6.1.3](#)), the use of concomitant medications is allowed at the investigator's discretion for management of toxicities.

### 6.2.1 Dose Modification for Treatment-emergent Adverse Experiences

The following actions are recommended after any of the TEAEs listed in [Table 6-4](#) occur.

- The investigator should notify the medical monitor acting on behalf of the sponsor about the TEAE within 24 hours of the awareness.
- The investigator should monitor the subject and if necessary, perform unscheduled diagnostic procedures and therapeutic interventions, including those not specified in the study protocol.
- If a subject experienced Grade  $\geq 2$  IRR, or another Grade  $\geq 2$  hypersensitivity event, Grade  $\geq 2$  CRS or Grade  $\geq 2$  CLS, then the investigator should obtain serum samples for

cytokines, complement, and histamine as soon as possible after the TEAE onset. These samples should be marked “STAT” and shipped immediately to the central laboratory.

- MT-3724 dose may be reduced at the investigator’s discretion. See [Table 6-3](#) for recommended dose reduction steps. The number of MT-3724 dose reductions per subject is not limited, except that the reduced dose cannot be < 5 µg/kg/dose (this is the lowest dose tested in the clinic so far).
- No intra-subject escalation of MT-3724 dose is permitted after previous MT-3724 dose reduction.
- MT-3724 treatment may be **restarted** if the TEAE that previously led to treatment modification has resolved to Grade ≤1 or the subject’s baseline within the time frame deemed appropriate at the investigator’s discretion.
  - After the resolution of the TEAE, the MT-3724 dose for continued treatment may be the same or reduced, as determined according to the stopping rules (if applicable) or at the investigator’s discretion

MT-3724 treatment must be **permanently discontinued** if a TEAE that previously led to treatment modification did not resolve to Grade ≤1 or baseline within 14 days.

**Table 6-3. Dose Reduction Steps**

Dose Reduction a	Dose µg/kg/dose		
	10	25	50
Full Dose			
First Reduction (~ 25%)	8	19	38
Second Reduction (~ 50%)	5	13	25

a Other reductions require consultation and agreement of the medical monitor.

**Table 6-4. MT-3724 Dose Modification Guidance and Specific Management of Toxicities**

		Specific Management	MT-3724 Dose Modification a
Neutropenia or Thrombocytopenia			
ANC AND Platelet	> 500/ $\mu$ l or < 500/ $\mu$ l for < 5 days $\geq$ 25,000/ $\mu$ l		No change
ANC AND / OR Platelet	< 500/ $\mu$ l for $\geq$ 5 days, OR febrile neutropenia c $<$ 25,000 for $\geq$ 7 days with or without active bleeding, OR $<$ 50,000/ $\mu$ l for $\geq$ 7 days with clinically significant bleeding b		Decrease by 1 dose level
Infusion-related Reaction or Other Hypersensitivity Event			
IRR OR Hypersensitivity reaction	Grade $\geq$ 2	Infusion must be interrupted.	Treatment may be restarted or permanently discontinued at the investigator's discretion.  If the MT-3724 re-treatment after Grade 2 IRR is allowed, then it must occur: 
 
Only after the appropriate delay (ie, resolution of symptoms).
 
At the reduced dose and/or reduced infusion rate, where both will be chosen at the investigator's discretion.
 
After the appropriate anti-allergic prophylaxis according to the premedication guidance in this protocol (see Section 6.1.2) or the institutional guideline.
 

	Grade $\geq$ 3		MT-3724 treatment must be permanently discontinued

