**Table 6-1. Step-up Dosing Schedule for Cohorts 1 and 2**

Day	MT-3724 Dose (µg/kg) a,b	
	Cohort 1 (n = 6)	Cohort 2 (n = 6)
Cycle 1 D1, D3	10	10
Cycle 1 D5, D8	25	25
Cycle 1 D10, D12	25	50
Cycle 2 D1, D3, D5, D8, D10, D12	25	50
Cycle 3+ D1, 8, 15 (weekly dosing)	25	50

a The total administered dose of MT-3724 must not exceed 1200 µg per infusion for the 10 µg/kg dose; 3000 µg per infusion for the 25 µg/kg dose and 6000 µg per infusion for the 50 µg/kg dose in all treatment cycles.

b Each dose of MT-3724 must be preceded by premedication administered within 60 minutes before the start of each infusion (see [Section 6.1.2](#)).

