**Table 6-4. MT-3724 Dose Modification Guidance and Specific Management of Toxicities**

		Specific Management	MT-3724 Dose Modification a
SCr increase $\geq$ 1.5-3.0 times above baseline or 1.5-3.0 x ULN in the absence of dehydration or bleeding			May trigger a modification of MT-3724 treatment (dose interruption, dose delay, dose reduction or permanent discontinuation) if deemed at least possibly related to MT-3724 by the investigator
Any Grade $\geq$ 3 electrolyte abnormality that does not resolve, with or without intervention, to Grade $<$ 2 within 72 hours			
Any other Grade $\geq$ 3 nonhematological toxicity excluding the following:	
 
• Nausea, vomiting, or diarrhea, if manageable with antiemetic or antidiarrheal agents within 7 days of onset
 
• Fatigue lasting <math>\leq</math> 72 hours
 
• Grade 3 laboratory abnormalities, if asymptomatic and without a clear clinical correlate
 
		
Hepatotoxicity			
AST and / or ALT OR Bilirubin	$\leq$ 5.0 x ULN (isolated) $\leq$ 1.5 x ULN (isolated)		
 
• No change in treatment
 
• Monitor subject
 

AST and / or ALT OR Bilirubin	$>$ 5 x ULN – 8.0 x ULN (for subjects enrolled with AST/ALT $<$ 3 x ULN) $>$ 1.5 x ULN – 5.0 x ULN		
 
• Temporarily or permanently (see next row) discontinue treatment
 
• Monitor subject
 
• Continue at dose reduced by 1 dose level after abnormal values resolve to Grade <math>\leq</math> 1 or baseline values
 

AST or ALT	$>$ 8.0 x ULN for any period of time (for any subject)		
 
• Permanently discontinue treatment
 

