**Table 6-4. MT-3724 Dose Modification Guidance and Specific Management of Toxicities**

		Specific Management	MT-3724 Dose Modification a
	> 5 x ULN for more than 2 weeks (for subjects enrolled with AST/ALT 3-5 x ULN)		
AST and / or ALT  AND  Bilirubin	> 3.0 x ULN (without findings of cholestasis defined as serum ALP < 2 × ULN)  > 2.0 x ULN or INR > 1.5		
 
• Permanently discontinue treatment
 

AST and / or ALT  OR  Bilirubin	> 3.0 x ULN with the appearance of fatigue, nausea, vomiting, right upper quadrant pain or tenderness, fever, rash, and/or eosinophilia (> 5%)  > 5.0 x ULN		
 
• Permanently discontinue treatment
 

NOTE: These are recommendations in situations where a possible relatedness to study drug is assumed. These recommendations cannot consider all clinical circumstances; therefore, the investigator is encouraged to contact the sponsor and/or medical monitors to discuss alternative courses of action.

The number of MT-3724 dose reductions per subject is not limited, except reductions beyond what is outlined in [Table 6-3](#) require consultation with the medical monitor.

ALP = alkaline phosphatase; ALT = alanine aminotransferase; ANC = absolute neutrophil count; AST = aspartate aminotransferase; BP = blood pressure; CLS = capillary leak syndrome; CRS = cytokine release syndrome; INR = international normalized ratio; IRR = infusion-related reaction; ULN = upper limit of normal; TEAE = treatment-emergent adverse event.

a MT-3724 dose reduction by 1 dose level translates to an approximate reduction by 25% to 33%, see [Table 6-3](#). The actual amounts for either agent will be determined by the investigator after consultation with sponsor and medical monitor.

b Clinically significant bleeding is that which requires platelet transfusion.

c Febrile neutropenia is defined as ANC < 1000/µl and fever (a single body temperature reading of > 38.3°C [> 101°F] or a sustained body temperature of ≥ 38.0°C [≥ 100.4°F] for more than 1 hour).

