#### Hematological Treatment-Emergent Adverse Events

- Grade  $\geq 3$  febrile neutropenia (absolute neutrophil count [ANC]  $< 1000/\mu\text{l}$  and a single body temperature reading of  $> 38.3^\circ\text{C}$  [ $101^\circ\text{F}$ ] or a sustained body temperature of  $\geq 38.0^\circ\text{C}$  [ $100.4^\circ\text{F}$ ] for more than 1 hour)
- Grade 4 neutropenia (ANC  $< 500/\mu\text{l}$ ) for  $> 5$  days; if the investigator determines that granulocyte colony-stimulating factor (G-CSF) therapy for Grade 4 neutropenia is essential within  $\leq 5$  days of onset, then this AE will also qualify as DLT
- Grade 3 thrombocytopenia ( $< 50,000/\mu\text{l}$  and  $\geq 25,000/\mu\text{l}$ ) with CS bleeding (ie, bleeding requiring platelet transfusion)
- Grade 4 thrombocytopenia ( $< 25,000/\mu\text{l}$ ) with or without bleeding
- Grade 4 anemia

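### Table 6-4 has no bleeding exception in its no-change row: with acceptable ANC, platelets of 25,000 to <50,000/µl with a transfusion-requiring bleed under 7 days are assigned no dose change

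*Protocol*

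**What the plan says.** Protocol Table 6-4 (section 6.2.1) handles neutropenia and thrombocytopenia in two rows.

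- **No-change row.** The neutrophil condition must be met (ANC above 500/µl, or below it for under 5 days) and platelets must be at least 25,000/µl. Bleeding is not mentioned.
- **Decrease row.** The dose falls one level for prolonged or febrile neutropenia, or for either of two platelet conditions: below 25,000 for at least "7 days with or without active bleeding, OR" below 50,000/µl for at least "7 days with clinically significant bleeding".

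Footnote b gives the definition: "Clinically significant bleeding is that which requires platelet transfusion".

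The DLT list in section 10.3.9 sets no minimum duration for platelet events. It includes Grade 3 thrombocytopenia (25,000 to <50,000/µl) "with CS bleeding (ie, bleeding requiring platelet transfusion") and Grade 4 thrombocytopenia (<25,000/µl) "with or without bleeding".

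Three other provisions bear on the point. Section 6.2 directs the investigator to Table 6-4 for dose modification. Section 6.5 allows platelet transfusion only once the investigator has considered whether MT-3724 should be modified for drug-related cytopenia. Section 6.2.1 allows a restart "if the TEAE that previously led to treatment modification has resolved to Grade" 1 or lower, or to the subject's baseline.

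**The concern.** Bleeding that needs a platelet transfusion is an acute event, and the DLT list treats it as potentially dose-limiting from onset. The dosing table nevertheless prints no change for it until the low count and bleeding have lasted 7 days. The investigator making the section 6.5 assessment is sent by section 6.2 to a row that advises continuing as planned.

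The printed action has a second effect. The section 6.2.1 restart condition applies only to an event that has already led to a treatment modification. No change is not a modification, so the row does not trigger the requirement to wait for recovery.

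Timing makes this matter most in Cohort 2. Table 6-1 raises the dose from 25 µg/kg on Day 8 to 50 µg/kg on "Cycle 1 D10, D12". As printed, the row would not stop that step in a subject who is bleeding; only the investigator's discretion would.

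**Working it through.** The plan gives no figure to reproduce. The check applies the printed rows to each combination of count, duration and bleeding, then compares the 7-day condition with the dosing calendar.

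**Row check.** Assume ANC above 500/µl and no febrile neutropenia. The no-change row applies if platelets ≥25,000/µl. The decrease row applies if platelets <25,000/µl for ≥7 days, or <50,000/µl for ≥7 days with clinically significant (CS) bleeding.

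| Platelets (/µl) | Duration | CS bleeding | Row(s) met | On DLT list (10.3.9) |
|---|---|---|---|---|
| 30,000 | 3 or 6 days | yes | no change only | yes |
| 30,000 | 7 or 10 days | yes | no change **and** decrease | yes |
| 30,000 | any | no | no change only | no |
| 15,000 | 3 or 6 days | yes or no | none | yes |
| 15,000 | 7 or 10 days | yes or no | decrease only | yes |

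The first two lines are the main fault and share one cause: the no-change row lacks a bleeding exception. The fourth line is the secondary gap.

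**Calendar check.** Inputs:

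- Cycle 1 doses fall on Days 1, 3, 5, 8, 10 and 12 (Table 6-1).
- Cohort 2 receives 10, 10, 25, 25, 50 and 50 µg/kg; Cohort 1 receives 10, 10, 25, 25, 25 and 25 µg/kg (Table 6-1).
- Hematology is scheduled on Days 1 and 8 (Table 1-1), so Day 8 is the only scheduled Cycle 1 count after the first dose.

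If the event is first documented on the Day 8 predose count, the 7-day condition is met on Day 8 + 7 = Day 15, or Day 14 if Day 8 counts as day 1. The doses before then are Days 8, 10 and 12, which is 3 of 6:

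- Cohort 2: 25, 50 and 50 µg/kg.
- Cohort 1: 25, 25 and 25 µg/kg.

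If the event is found just after the Day 8 dose, 2 doses remain (Days 10 and 12).

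More generally, for onset on day s, count the doses on days d with s < d < s + 7:

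| Onset day | 1 | 2 | 3 | 4 | 5 | 6 | 7 | 8 | 9 | 10 | 11 |
|---|---|---|---|---|---|---|---|---|---|---|---|
| Doses in window | 2 | 3 | 2 | 3 | 2 | 3 | 3 | 2 | 2 | 1 | 1 |

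For any onset from Day 1 to Day 11, therefore, 1 to 3 scheduled Cycle 1 doses fall in the period for which the platelet rows say no change or say nothing.

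**The case against.** The strongest reply is that the table is not the whole safety system. Its own note calls the entries recommendations that cannot cover every circumstance and encourages contact with the sponsor or medical monitor. Sections 6.2 and 6.2.1 let the investigator interrupt, delay, reduce or stop treatment at any time. Section 6.2.1 also asks for the medical monitor to be told within 24 hours of a listed event. Section 6.5 makes a modification assessment a condition of platelet transfusion, which by definition every bleed of this kind requires. At 7 days or more, a sensible reader would follow the more specific decrease row. An investigator would probably also fill the missing row for short, very low counts.

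Much of this stands, and it keeps the impact small. It does not correct the printed default: the section 6.5 assessment is referred back to this table, and the answer there is no change.

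Four stronger readings are tempting, and the documents do not support them.

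- *Every transfusion-requiring bleed under 7 days is told no change.* Below 25,000/µl no platelet row applies, and the no-change row also needs the ANC condition. A bleed that is itself Grade 3 or worse may come under the entry for any other Grade ≥3 "nonhematological toxicity excluding the following", which may trigger a modification.
- *The mismatch with the DLT list is itself an error.* The list serves cohort decisions and the table serves individual dosing, so their thresholds may differ.
- *Bleeding subjects will be stepped up to 50 µg/kg.* The row fails to stop the step; it does not order it over the investigator's judgment.
- *The 7-day condition should go altogether.* Section 6.2.1 bars re-escalation after a reduction, so one short event could hold a step-up subject at a low dose permanently. A 7-day threshold for a mandatory decrease is defensible.

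**Conclusion.** The concern holds for the platelet rows of Table 6-4, given acceptable ANC. A transfusion-requiring bleed at 25,000 to <50,000/µl is assigned no change for under 7 days and two conflicting actions thereafter. The absence of any row for platelets below 25,000/µl for under 7 days is real but secondary.

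The impact is minor. The 1 to 3 doses affected per event assume dosing on the scheduled days and no discretionary hold; they count doses for which the platelet rows give no instruction to modify, and do not predict that those doses would be given. The documents supply no rate of thrombocytopenia or bleeding, and section 2.2.1 does not name thrombocytopenia among the important risks, so few subjects may be affected. DLT counting, cohort decisions and efficacy endpoints are untouched. The case for acting is that the fault concerns subject safety, is specific and is cheap to remove.

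**What to change.** Amend the platelet rows of Table 6-4 as follows.

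1. Limit the no-change row to platelets ≥25,000/µl without clinically significant bleeding. Word the exception to apply below 50,000/µl, so that higher counts are not left without a row.
2. Add a row for platelets <50,000/µl with clinically significant bleeding, or <25,000/µl with or without bleeding, lasting under 7 days. The action is to hold MT-3724 until bleeding stops and platelets recover to Grade ≤1 or baseline, notify the medical monitor, and then resume at the same or a reduced dose under section 6.2.1.
3. Keep the 7-day threshold for the mandatory one-level decrease.

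The 30,000/µl bleeding case then maps to a hold before 7 days and to the decrease alone from 7 days on, and the 15,000/µl short-duration case has a row.

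The cost is table wording in the next amendment and a few more dose delays. Because a hold is a treatment modification, the section 6.2.1 rule would also apply: permanent discontinuation if the event has not resolved to Grade ≤1 or baseline within 14 days. The sponsor should accept that consequence knowingly.
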